Grade 1	Reduce to 50% of the original infusion rate or interrupt the infusion until the infusion reaction resolves	For grade 1–2 events: 
 - Administer acetaminophen and/or antihistamine according to local clinical practice based on the investigator' judgment
Grade 2	Reduce to 50% of the original infusion rate or interrupt the infusion until the infusion reaction resolves, then resume at 50% of the original infusion rate	
 - Consider prophylactic premedications for subsequent infusion according to local clinical practice
Grade 3/4	Permanently discontinue	For grade 3–4 events: 
 - Manage severe infusion-related reactions according to local clinical practice (e.g. administration of epinephrine, diphenhydramine, ranitidine, and glucocorticoids)

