5.3 Administration Adjustments of Investigational Drug

5.3.1 General principles

- The subject's hematologic, hepatic, and renal function must meet the requirements for administration of study treatment prior to each dose. All the toxicities must resolve to NCI CTCAE v4.03 grade 0–1 or baseline levels (excluding alopecia, fatigue, etc.).
- Reasons for administration adjustments and actual changes shall be documented in the original medical records and electronic case report forms (Electronic case report form , eCRFs).

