5.3.2 Administration adjustments of IBI308

Dose adjustments of IBI308 are not permitted throughout the trial. Refer to the following table for administration adjustments of IBI308 (only for AEs related to IBI308 as determined by the investigator).

Table 3. Administration adjustments of IBI308

AEs	Severity	Administration Adjustments
Pneumonitis	Grade 2 pneumonitis	Interrupt ^a
	Grade 3 or 4 pneumonitis	Permanently discontinue
Diarrhea or Enterocolitis	Grade 2 or 3 diarrhea or enterocolitis	Interrupt ^a
	Grade 4 diarrhea or enterocolitis	Permanently discontinue
Dermatitis	Grade 3 dermatitis	Interrupt ^a
	Grade 4 dermatitis	Permanently discontinue
Hepatitis	Grade 2 AST, ALT, or TBIL elevation for subjects with normal AST, ALT or TBIL at baseline; AST, ALT, or TBIL elevation of $\geq 50\%$ for < 7 days for subjects with AST, ALT, or TBIL $> \text{ULN}$ at baseline	Interrupt ^a
	Grade 3 or 4 AST, ALT, or TBIL elevation for subjects with normal AST, ALT or TBIL at baseline; AST, ALT, or TBIL elevation of $\geq 50\%$ for ≥ 7 days for subjects with AST, ALT, or TBIL $> \text{ULN}$ at baseline	Permanently discontinue
Hypophysitis	Grade 2 hypophysitis	Interrupt ^b
	Grade 3 or 4 hypophysitis	Permanently discontinue
Adrenocortical insufficiency	Grade 2 adrenocortical insufficiency	Interrupt ^b
	Grade 3 or 4 adrenocortical insufficiency	Permanently discontinue
Hyperthyroidism	Grade 3 or 4 hyperthyroidism	Permanently discontinue
Type I Diabetes	Grade 3 hyperglycemia	Interrupt ^b
	Grade 4 hyperglycemia	Permanently discontinue
Renal insufficiency	Grade 2 or 3 Cr elevation	Interrupt ^a
	Grade 4 Cr elevation	Permanently discontinue
Neurotoxicity	Grade 2 neurotoxicity	Interrupt ^a

AEs	Severity	Administration Adjustments
	Grade 3 or 4 neurotoxicity	Permanently discontinue
Infusion Reactions	Grade 3 or 4 infusion reaction	Permanently discontinue
Other AEs	First occurrence of other grade 3 AEs	Interrupt ^a
	Second occurrence of other grade 3 AEs	Permanently discontinue
	Grade 3 AE that cannot resolve to grade 0–2/baseline levels within 7 days or grade 0–1/baseline levels within 14 days	Permanently discontinue
	Grade 4 AE	Permanently discontinue ^c

a: Resume the investigational drug after symptoms resolve to grade 0–1 or baseline levels.

b: Resume the investigational drug if hypophysitis, adrenocortical insufficiency, or type I diabetes is adequately controlled and require only physiological hormone replacement.

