c: For grade 4 laboratory abnormalities, the event shall be determined based on clinical signs/symptoms and the clinical judgment of the investigator.

Investigational drug is allowed to be interrupted for up to 6 weeks. If the symptoms do not resolve within 6 weeks and treatment cannot be resumed, the subject must permanently discontinue IBI308 treatment and enter the follow-up phase of the study. Except for the following two cases:

- IBI308 interruption > 6 weeks due to glucocorticoid reduction for irAEs: Consult the sponsor's medical manager prior to resuming IBI308. Tumor imaging evaluation for efficacy shall not be affected by treatment interruption and will be performed as scheduled.
- IBI308 interruption > 6 weeks due to AEs possibly related or unrelated to IBI308: Consult the sponsor's medical manager prior to resuming IBI308. Tumor imaging evaluation for efficacy shall not be affected by treatment interruption and will be performed as scheduled.

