	Grade 3	Interrupt – Resume treatment after blood glucose is under control	For grade 3–4 events: 
 – Consult with sponsor's medical manager – Monitor and assess pancreas islet function – Consider consulting an endocrinologist – Blood glucose control with insulin, adjust insulin dose accordingly – If ketoacidosis occurs, subjects shall be hospitalized to receive insulin, fluid replacement, and alkali therapy
	Grade 4	Permanently discontinue	
Renal Insufficiency (Creatinine Elevated)	Any grade		
 – Monitor signs and symptoms closely (e.g. oliguria, dark urine, anemia, fatigue, and weight loss) – Subjects shall be fully evaluated to rule out any alternative causes – Monitor and evaluate renal function – Consider consulting a nephrologist – Consider kidney biopsy when necessary to distinguish between inflammatory and non-inflammatory causes
	Grade 1	No dose adjustments required	For grade 1 events: 
 – Monitor creatinine levels Q1W – If creatinine level returns to baseline level, resume routine creatinine monitoring according to the study protocol

	AE Grade/Administration Adjustments		Toxicity Management
	Grade 2 or 3	Interrupt 
 • If reduces to grades 0–1 or baseline, continue the treatment at the next scheduled date • If persists for > 7 days or worsens, treat as a grade 4 event 	For grade 2–3 events: 
 – Discuss with sponsor's medical manager – Monitor creatinine levels every 2–3 days – Begin systemic glucocorticoid treatment based on experience – If reduces to grade 1, taper glucocorticoid for at least 1 month, consider prophylactic antibiotic to prevent infections – Consider kidney punch biopsy – Consult a nephrologist
	Grade 4	Permanently discontinue	For grade 4 events: 
 – Discuss with sponsor's medical manager – Monitor creatinine levels once daily – Begin systemic glucocorticoid treatment based on experience – If reduces to grade 1, taper glucocorticoid for at least 1 month, consider prophylactic antibiotic to prevent infections – Consult a nephrologist – Consider kidney punch biopsy

	AE Grade/Administration Adjustments		Toxicity Management

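### For immune-related grade 2–3 creatinine elevation and grade 3 dermatitis, Table 3 and Appendix 7 of the protocol set different permanent-stop rules, and no clause says which prevails

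*Protocol*

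**What the plan says.** **Table 3 (protocol 5.3.2).** Its scope is "only for AEs related to IBI308 as determined by the investigator". The renal row lists "Grade 2 or 3 Cr elevation" as an interruption and grade 4 as a permanent stop. The dermatitis row lists "Grade 3 dermatitis" as an interruption and grade 4 as a permanent stop. Both interruptions carry footnote a: "Resume the investigational drug after symptoms resolve to grade 0–1 or baseline levels".

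**Outer time limit.** Section 5.3.2 puts a six-week cap on interruption: "If the symptoms do not resolve within 6 weeks and treatment cannot be resumed, the subject must permanently discontinue IBI308 treatment". Two exceptions follow, each requiring consultation with the sponsor's medical manager. Section 4.4, item 8 also withdraws subjects whose treatment is delayed 6 weeks by adverse reactions, and it gives no exceptions.

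**Appendix 7, Table 1.** The row for grade 2 or 3 renal insufficiency interrupts and allows treatment to continue after recovery, but adds: "If persists for > 7 days or worsens, treat as a grade 4 event". The grade 4 row is permanent discontinuation. The grade 3 dermatitis row interrupts, but requires permanent discontinuation if the rash is not down to grade 0–1 or baseline within 30 days.

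**Routing.** Sections 1.3 and 4.4 point toxicity decisions to section 5.4. Section 5.4 points irAE dose adjustments to Appendix 7, and the scope line of Appendix 7 sends irAEs to that guideline. Section 7.8.1, on irAEs, cites sections 5.3 and 5.4 and then names Appendix 7 as the detailed guide.

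**The concern.** An immune-related renal or skin event is also an event related to IBI308, so it falls under both tables. For some courses of the event, one table tells the investigator to resume and the other to stop for good. At stake is whether a patient is re-exposed to a checkpoint inhibitor after an immune toxicity. The choice also feeds the summaries of adverse events leading to treatment discontinuation (protocol 8.4.6.2; SAP 5.6.1). Two sites could each follow the protocol and make opposite decisions.

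**Working it through.** The plan states no figure to reproduce, so the check is a comparison of texts. Only events that are both related to IBI308 and immune-related are at issue; other related events fall under Table 3 alone.

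| Event | Table 3 with footnote a | Appendix 7, Table 1 |
|---|---|---|
| Grade 2–3 creatinine, persisting | Interrupt; resume on recovery; outer limit 6 weeks | Permanent stop once it lasts more than 7 days |
| Creatinine worsening from grade 2 to grade 3 | Still an interruption; resume on recovery | Permanent stop on worsening |
| Grade 3 dermatitis, persisting | Interrupt; resume on recovery; outer limit 6 weeks | Permanent stop if not recovered within 30 days |

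**Step 1: a case that needs no clock.** Creatinine rises to grade 2, then grade 3, then returns to grade 0–1 inside the 6-week limit. Table 3 puts grades 2 and 3 in the same interrupt row, so footnote a directs resumption. Appendix 7 treats the worsening as grade 4, so the drug is stopped.

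**Step 2: cases that turn on duration.** The 6-week limit is 6 × 7 = 42 days. A grade 2 creatinine rise that lasts 14 days from onset and resolves is inside 42 days and is resumed under Table 3. Since 14 > 7, Appendix 7 stops it. A grade 3 rash that passes the 30-day limit but clears before the 6-week limit is likewise resumed under one table and stopped under the other (30 < 42).

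**Step 3: does another part of Table 3 close the gap?** Table 3 does set shorter limits, but elsewhere. The hepatitis row splits at 7 days for subjects with raised baseline values, matching Appendix 7. The rows for other AEs stop a grade 3 event that has not reached grade 0–2 or baseline in 7 days, or grade 0–1 or baseline in 14 days. Neither limit reaches the named renal or dermatitis rows. A reader who sees limits stated there has no reason to suppose an unstated one here.

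**Step 4: is precedence stated?** The routing in 1.3, 4.4, 5.4, 7.8.1 and the Appendix 7 scope line favors Appendix 7 for irAEs. Against that, Table 3 does not exclude irAEs, and 7.8.1 also cites section 5.3, which contains Table 3. None of these places says which rule yields when they differ.

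**The case against.** The strongest reply is that the texts can be read together. Six weeks is an outer cap, not a right to resume at any time within it, and a site can comply with both texts by applying the stricter stop. Appendix 7 is the specific rule for irAEs and Table 3 the general one. The Appendix 7 entries for grade 2–3 creatinine and grade 3 rash also call for discussion with the sponsor's medical manager.

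Much of this stands. Reading Appendix 7 as the governing irAE rule is sensible and would settle the matter in practice, and central discussion limits variation between sites. It does not remove the conflict. Footnote a is an instruction to resume on recovery, and for creatinine moving from grade 2 to grade 3 Table 3 is not silent: it classes both grades as interruptions. Discussion with the medical manager does not say which rule applies.

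Three stronger readings are tempting but unsupported:

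- **Fixed windows of conflict.** A reader might subtract 7 or 30 days from 42 and report exact windows. That assumes a common clock. The 6-week limit counts interruption, which under 3-weekly dosing need not begin at event onset. The endpoint is also unclear, because 5.3.2 has exceptions and 4.4, item 8 has none.
- **Appendix 7 as optional.** Its General Principles do recommend managing irAEs by the table, but that sentence is in the toxicity-management column. The stop rules are in the administration-adjustment column and are worded as directions.
- **Endocrine rows as a further conflict.** For grade 2 hypophysitis and adrenocortical insufficiency, footnote b of Table 3 resumes once the event is "adequately controlled and require only physiological hormone replacement", while Appendix 7 asks for grade 0–1 or baseline. These differ only if a controlled event still grades above 1 and above baseline, which the documents do not settle.

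**Conclusion.** Wrong as written, and minor: an internal inconsistency in a dosing-safety rule, confined to two immune-related toxicities. The finding rests on the wording alone. The creatinine case of grade 2 worsening to grade 3 needs no assumption about when any clock starts; the 14-day example assumes that persistence is counted from onset.

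The practical effect is on re-exposure after an immune renal or skin event and on a descriptive safety count. A reader might infer a threat to the efficacy conclusion. The documents do not support that: neither rule enters the definition of ORR, its test or the sample size. The documents give no rate for these events, and the protocol's Summary of Amendment reports 28 subjects enrolled, so the number affected may be small or zero.

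**What to change.** In section 5.3.2, state that for irAEs the stop rules and time limits of Appendix 7 take precedence over Table 3. Annotate the Table 3 renal row with the stop for persistence beyond 7 days or worsening, and the dermatitis row with the 30-day stop for grade 3 rash. Mark both notes as applying to irAEs only, so that related events that are not immune-related keep the present rule. The endocrine rows and section 5.3.1 need no change on this account.

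The cost is one sentence and two row notes, made in the protocol text or a clarification letter, with no added visits or procedures.

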7.8 Managing of Drug-Related Toxicities

During the course of the trial, the sponsor will conduct regularly monitoring of safety. Detailed information regarding the frequency of review and type of data to be reviewed will be presented in a separate safety review plan.

7.8.1 irAEs

Since the mechanism of action of IBI308 involves T-cell activation and proliferation, irAEs are likely to be observed during this study. Refer to Section 5.4 for the definition of an irAE. Signs and symptoms of irAEs shall be monitored.

Refer to Sections 5.3 and 5.4 for administration adjustments and management of AEs of IBI308. Refer to Appendix 7 (Tables 1 and 2) for a detailed guide on irAE management.

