	Grade 3 or grade 4	Permanently discontinue	
Myasthenia Gravis
 
 – Glucocorticoids may be used to treat myasthenia gravis (shall be used under the supervision of a neurologist since corticosteroids, especially high-dose, may result in initial exacerbation of symptoms) – Subjects intolerant to glucocorticoids may be treated with plasmapheresis or IVIgG – For myasthenia gravis-like neurotoxicities, consider acetylcholinesterase inhibitors in addition to glucocorticoids 
Guillain-Barre Syndrome
 
 – Plasmapheresis or IVIgG should be considered for subjects with Guillain-Barré syndrome (glucocorticoids are generally ineffective)

Table 2. IBI308 administration adjustments and toxicity management of other potential irAEs

	CTD Grade/Administration Adjustments	Toxicity Management
Any grade	Dose adjustments are not required for AEs unrelated to study treatment or laboratory abnormalities that are not clinically significant (events caused by underlying disease)	Manage based on local clinical practice
Grade 1	No dose adjustments required	
Grade 2	Consider interruption until reduces to grade 0–1 or baseline	
Grade 3	
 • First occurrence: interrupt until reduces to grade 0–1 or baseline • Second occurrence: permanently discontinue • For an AE that reduces to grades 0–2 within 7 days, or grades 0–1 or baseline within 14 days, interrupt and then resume the treatment at the next scheduled date Otherwise, permanently discontinue 	
Grade 4	Permanently discontinue (Note: for grade 4 laboratory abnormalities, the event shall be determined based on clinical signs/symptoms and the clinical judgment of the investigator)	

Table 3. Dose adjustments and toxicity management for infusion reactions

CTD Grade	Administration Adjustments	Toxicity Management
Any grade		
 - Manage based on local clinical practice - Monitor infusion-related reactions (e.g. fever or chills, flushing and/or pruritus, changes in heart rate and blood pressure, dyspnea, chest discomfort, rash, etc.) and allergic reactions (e.g. systemic urticaria, angioedema, asthma, hypotension, tachycardia, etc.)

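### Appendix 7 Table 2, Grade 3 (other potential irAEs): the third bullet, read literally, lets IBI308 resume at grade 2, while three other dosing rules require grade 0–1 or baseline

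*Protocol*

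**What the plan says.** Appendix 7 Table 2 covers potential immune-related events that have no row in Appendix 7 Table 1. Its Grade 3 cell has three bullets:

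- First bullet: "First occurrence: interrupt until reduces to grade 0–1 or baseline".
- Second bullet: permanent discontinuation on a second occurrence.
- Third bullet: "For an AE that reduces to grades 0–2 within 7 days, or grades 0–1 or baseline within 14 days", followed by the action "interrupt and then resume the treatment at the next scheduled date Otherwise, permanently discontinue".

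Three places in the body of the protocol bear on the same event:

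- Section 5.3.1, in the bullet on conditions before each dose: "All the toxicities must resolve to NCI CTCAE v4.03 grade 0–1 or baseline levels (excluding alopecia, fatigue, etc".
- Section 5.3.2 Table 3 marks a first occurrence of another grade 3 AE as an interruption under footnote a, which says "Resume the investigational drug after symptoms resolve to grade 0–1 or baseline levels".
- Section 5.3.2 Table 3 also lists, as grounds for permanent discontinuation, "Grade 3 AE that cannot resolve to grade 0–2/baseline levels within 7 days or grade 0–1/baseline levels within 14 days".

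Section 7.8.1 sends sites to both sources: "Refer to Sections 5.3 and 5.4 for administration adjustments and management of AEs of IBI308" and "Refer to Appendix 7 (Tables 1 and 2) for a detailed guide on irAE management". Neither is said to take precedence.

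**The concern.** The third bullet offers two routes back to treatment, joined by *or*. The first needs only a fall to grade 2 within 7 days, so a site following it as written may give the next infusion while the event is still grade 2. The bullet two lines above it, footnote a and Section 5.3.1 do not allow that.

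This catch-all cell governs re-exposure after a grade 3 event that the protocol has not otherwise planned for. Uveitis is one: it has no row in Section 5.3.2 Table 3 or in Appendix 7 Table 1, yet Section 7.8.2 makes it an event of special interest from grade 2 upward. At stake are re-dosing safety and uniform handling across sites. The efficacy analysis is not involved.

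**Working it through.** The plan states no figure on this point, so the check sets the rules side by side and then works one case through them.

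**Rules compared.** Take a first occurrence of a drug-related grade 3 event with no row of its own, baseline below grade 2, and not one of the Section 5.3.1 exceptions.

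| Source | Level needed to resume | Role of the 7- and 14-day limits |
|---|---|---|
| Appendix 7 Table 2, Grade 3, first bullet | grade 0–1 or baseline | none |
| Appendix 7 Table 2, Grade 3, third bullet | grade 0–2 by day 7, or grade 0–1/baseline by day 14 | condition for resuming; otherwise stop |
| Section 5.3.2 Table 3, footnote a | grade 0–1 or baseline | none |
| Section 5.3.2 Table 3, other grade 3 AEs, unresolved | not stated | trigger for stopping only |
| Section 5.3.1 | grade 0–1 or baseline | none |

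**Worked case.** The dose is on cycle day 1. Table 1 puts the next dose on day 22 ± 3, a window of days 19 to 25. Two things are assumed. The clocks start at onset of grade 3, because neither table says when they start. The durations are chosen for illustration, because the documents give none.

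- Onset on cycle day 15; grade 2 after 5 days; grade 1 after 14 days.
- Grade 2 is reached on day 15 + 5 = 20 and grade 1 on day 15 + 14 = 29. The window closes on day 25, so the event is grade 2 throughout days 20 to 25.
- Deadlines: 5 ≤ 7 and 14 ≤ 14. Neither is missed, so no reading of the stopping rule applies.
- Third bullet: resume on day 22. First bullet, footnote a and Section 5.3.1: hold.

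The permitted grade at dosing is the only difference between the rules here.

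**How often the timing falls this way.** Let d be the cycle day of onset, t2 the days to grade 2 or less, and t1 the days to grade 1 or less (or baseline). The rules diverge if d + t2 ≤ 22 (grade 2 by the nominal date) and d + t1 > 25 (not grade 1 by the end of the window).

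| (t2, t1) | Onset days that diverge | Count of 21 | Count if day 25 is used for both limits |
|---|---|---|---|
| (5, 14) | 12–17 | 6 | 9 (days 12–20) |
| (7, 14) | 12–15 | 4 | 7 (days 12–18) |
| (5, 10) | 16–17 | 2 | 5 (days 16–20) |

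The counts show that the divergence can occur in ordinary dosing. They move by 3 days with the choice of cut-off and rest on assumed durations, so they are not estimates of risk.

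**The case against.** The strongest reply is that the rules can be applied together. Section 5.3.1 is headed as general principles and is mandatory. The first bullet sets the same level inside the very cell at issue. The third bullet ends in permanent discontinuation, and Section 5.3.2 Table 3 uses the same 7- and 14-day limits purely as a reason to stop. On that view the third bullet only separates interruption from permanent stop, the other rules fix the level for resuming, and no precedence clause is needed. This is probably what was meant. It does not remove the defect, because the bullet does not say so: its action clause is an instruction to resume.

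A reader might infer that grade 2 re-dosing is an isolated slip against three consistent rules. The tally is not that clean. The Grade 2 row of the same table only asks that interruption be considered, which leaves dosing at grade 2 to discretion and itself sits awkwardly with Section 5.3.1. Against that, the general-principles row of Appendix 7 Table 1 interrupts at grade 2 and continues at grade 0–1 or baseline.

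A reader might also infer that the Table 3 stopping row contradicts the third bullet, so that an event still at grade 2 past day 14 could be resumed, held or stopped. That needs the reading on which missing either deadline is enough. If both must be missed, the row matches the bullet's closing clause, apart from an added mention of baseline in the 7-day condition. The wording is open, and the choice is clinical.

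**Conclusion.** The inconsistency is real and narrow. As written, the third bullet permits a dose at grade 2 that the first bullet of its own cell, footnote a and Section 5.3.1 do not. It should be corrected because a site that follows it literally gets a less cautious result than the protocol's general requirement.

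The documents do not support saying that the sponsor intended grade 2 re-dosing; the Table 3 row points the other way. Nor do they support a figure for how many subjects would be exposed. The case needs a first-occurrence, drug-related grade 3 event without its own row, with baseline below grade 2, outside the Section 5.3.1 exceptions, down to grade 2 within 7 days and still there through the next dosing window. The Summary of Amendment reports 28 subjects enrolled at the pause, so the number is likely small. ORR, its confidence interval, alpha and power are unaffected.

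**What to change.** In the third bullet of the Appendix 7 Table 2 Grade 3 cell, replace the instruction to interrupt and then resume with: *interrupt, and resume at the next scheduled date only once the event is grade 0–1 or baseline (Section 5.3.1)*.

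Leave the 7- and 14-day discontinuation wording in that bullet and in Section 5.3.2 Table 3 as it stands. Whether missing one deadline or both triggers discontinuation, and when the clocks start, are questions for the sponsor's clinical team. Check the Table 2 Grade 2 row against Section 5.3.1 in the same amendment.

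The cost is one clause of protocol text, with no change to data collection, sample size or analysis. The downside is that a few subjects may have a dose delayed. In the worked case, taken as cycle 1, dosing could move from day 22 to the following scheduled date, day 43: 43 − 22 = 21 days, within the six-week interruption limit in Section 5.3.2.
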